4.3.1. Study discontinuation (if applicable) n/a

4.3.2. Concomitant medication (if applicable) n/a

4.4. Risks and Benefits

n/a (data collection completed at prior institution; currently analyzing de-identified data only)

5 – Methods

Sample Size Justification and Power Analysis. We enrolled 125 primary care providers and 553 patients. Power calculations were performed via simulation studies with a two-sided significance level set to 0.05. These power simulations accounted for the anticipated subsamples for the patient behavioral outcomes (for example, stage of readiness for smoking cessation and the fact that only current smokers will contribute data for this outcome). Based on this sample size, we are appropriately powered for fully testing the associations in Aims 1 and 2 with at least 80% power. Specifically, for the continuous outcomes, we are appropriately powered for testing the effect of an unbalanced binary variable with prevalence 25% or 75% and an adjusted standardized coefficient of at least 0.2, based on a linear mixed-effects model. Additionally, we are sufficiently powered in terms of the binary outcomes of the aims, for testing the effect of an unbalanced binary independent variable with a prevalence of 25% or 75% and an (adjusted) odds ratio (OR) at least 2.5, using a mixed-effects logistic model. The tests for the continuous independent variables are expected to be more powerful for a given effect size in both continuous and binary outcomes.

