Quantitative Data Analysis and Interpretation. Our analyses were being defined *a priori* to address the study aims. We are using descriptive statistics such as means, standard deviations, and frequency distributions to examine data quality, identify patterns of missing and out-of-range values, and evaluate the assumptions of statistical tests. Remediation of normal distribution assumption violations will be accomplished using methods such as Box-Cox family transformations, or other methods as appropriate. Assessment of internal consistency reliability of all scales will be carried out using the Cronbach's alpha coefficient. Continuous outcomes (Aims 1 and 2) will be analyzed based on linear mixed effects models, with a random intercept according to the clinician, to account for the association between patients within the same clinician. Secondary analyses of item level components, consisting of Likert scale data, will be analyzed using Generalized Estimating Equations, which allow for the use of distributions in the Exponential Family other than the Normal Distribution. This will allow for the testing and use of the appropriate probability distribution to be used, while also accounting for the association between patients within the same clinician. Model selection for analyses focused on correlates of decision quality and screening completion will be based on Akaike's Information Criterion (AIC), instead of the usual statistical significance level (to avoid type I error inflation); this approach has been shown to lead to optimized models. We will only consider the statistical significance of each independent variable in the final models if the corresponding overall model test is significant at an alpha=0.05.

Patient-Provider Data Analyses. We are conducting a planned secondary analysis for physicians who have patients who respond to the survey (an estimated 40% of the total number of patients). We will perform a multilevel analysis using a model that contains

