5.4. Assignment / randomization (if applicable)

n/a

5.5. Section of instruments (to include for all studies with a social behavioral intervention) - *data has already been collected at prior institution; currently analyzing de-identified data only*

Table 2. Measures (Clinician Survey and Patient Survey) and Sources of Data			
Construct (Variables)	Source	Instrument	α
Clinician-Level (survey component takes approximately 15 minutes to complete)			
Personal Characteristics (demographics, clinician type, specialty, time since graduation, time in system)	Survey	Investigator-Developed Survey	
Attitudes (lung cancer screening, SDM, toward referring patients for screening)	Survey	Investigator-Developed Survey	
Barriers (lung cancer screening, SDM)	Survey	Investigator-Developed Survey	
Knowledge	Survey	Investigator-Developed Survey	
Subjective Norms	EHR	Assessed with LCS referral propensity of clinicians in same clinic	
Lung Cancer Screening Referral Propensity	EHR	{Total # LCS-eligible patients referred for LCS in past 12 mo} divided by {Total # LCS-eligible patients seen by clinician past 12 mo}	
HEDIS Scores; Clinician Smoking Cessation Referral Rate; Length of Clinician-Patient Relationship; Visit Characteristics (type, length of visit); Clinic Size; Clinician Panel Characteristics (% screening-eligible patient population)	EHR		
Documented SDM Discussion (high/low)	EHR		
Patient-Level (informed by our prior work, this survey takes approximately 30 minutes to completed) ^{50,55}			
Demographics (education, income); Health Status Characteristics (health status, family hx lung cancer); Cost	Survey	Investigator-Developed Demographic Survey	
Cognitive Variable (Knowledge)	Survey	9-item Likert Knowledge: Lung Cancer & Screening Scale	
Cognitive Variable (Literacy)	Survey	3-item Likert Health Literacy Screening Questionnaire ⁸¹	
Cognitive Variable (Numeracy)	Survey	8-item Likert Subjective Numeracy Scale ⁸²	
Psychological Variable (Stigma)	Survey	5-item Cataldo Lung Cancer Stigma Scale-Smoking Subscale ⁷⁸	0.89
Psychological Variable (Mistrust)	Survey	5-item Patient Trust in Medical Profession Scale ⁸⁰	0.84
Health Belief (Perceived Risk)	Survey	3-item Perceived Risk of Lung Cancer Scale ⁵⁵	0.88
Health Belief (Perceived Benefits)	Survey	6-item Perceived Benefits of Lung Cancer Screening Scale ⁵⁵	0.76
Health Belief (Perceived Barriers)	Survey	17-item Perceived Barriers to Lung Cancer Screening Scale ⁵⁵	0.87

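### Two clinic-level measures are listed as clinician factors, but no model has a clinic term; if they are tested and outcomes vary between clinics, type I error may exceed 5%

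*Combined protocol and SAP*

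**What the plan says.** - Section 5, Quantitative Data Analysis and Interpretation: continuous outcomes in Aims 1 and 2 use a linear mixed model "with a random intercept according to the clinician, to account for the association between patients within the same clinician". The item-level GEE analyses also cluster by clinician only.
- Section 5, Patient-Provider Data Analyses: the linked secondary analysis nests patients within providers, for continuous and binary outcomes alike. It names physician-level and patient-level variables and no clinic level.
- Section 5, Sample Size Justification: binary outcomes are to use a mixed-effects logistic model; no clinic effect is mentioned.
- Section 5.5, Table 2, clinician-level block: subjective norms are "Assessed with LCS referral propensity of clinicians in same clinic", and a later row includes "Clinic Size; Clinician Panel Characteristics".
- Section 3.3: Aim 1 seeks clinician factors that predict the three outcomes. Hypothesis 1 names knowledge, two attitudes, barriers and the clinician's own referral propensity. Neither subjective norms nor clinic size is among them.
- Section 4.1.2 counts one study site. The number of clinics within it is not stated, nor is any ICC.

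**The concern.** Patients are nested in clinicians, and clinicians in clinics. Clinic size is the same for every clinician in a clinic, and subjective norms are the same or nearly so. A model whose only random effect is the clinician treats clinicians in one clinic as independent replicates of an exposure that varies only between clinics. Any outcome variance shared within a clinic is then averaged over too many units, and the standard error of the clinic-level coefficient comes out too small.

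At stake is whether the study names clinic norms or clinic size as predictors by chance. Its results are meant to guide new decision-support tools, so such a finding could misdirect that work.

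**Working it through.** **The plan's own figure.** The plan gives no error rate for clinic-level predictors. Its one figure is power: "we are appropriately powered for fully testing the associations in Aims 1 and 2 with at least 80% power". Read as a coefficient per SD, 0.2 at 553 patients gives 0.2 × √553 / √(1 − 0.04) − 1.96 = 2.84, or 99.8% power without clustering. Read as a group difference in SDs with a 25:75 split, the standard error is √(1/138.25 + 1/414.75) = 0.0982, and 0.2/0.0982 − 1.96 = 0.08, or 53%. Without the ICC, the subsample sizes and the meaning of the coefficient, the claim can be neither confirmed nor refuted. It does not bear on the clinic level.

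**Inputs from the documents.** "We enrolled 125 primary care providers and 553 patients" (Section 5; the Summary gives 552 patients, which is immaterial here). Two-sided alpha is 0.05. The linked share is 40%, read as a share of patients: 0.40 × 553 = 221.

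**Assumptions.** Clinician ICC d = 0.05; clinic ICC c from 0 to 0.05; K = 15, 25 or 35 clinics; all 553 patients spread over the 125 clinicians; 50 clinicians in the linked subset; Wald test at 1.96.

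**Formula.** Set total outcome variance to 1, with m clinicians per clinic and n patients per clinician.

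- True variance of a clinic mean: c + d/m + (1 − c − d)/(mn).
- Variance implied by the clinician-only model, which absorbs c into the clinician variance and treats clinicians as independent: (c + d)/m + (1 − c − d)/(mn).
- Standard-error ratio r = √(implied/true). Type I error = 2Φ(−1.96 r).

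**Worked case, K = 25 and c = 0.05.** m = 125/25 = 5; n = 553/125 = 4.424; mn = 22.12.

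- True: 0.05 + 0.01 + 0.90/22.12 = 0.1007.
- Implied: 0.10/5 + 0.90/22.12 = 0.0607.
- r = √(0.0607/0.1007) = 0.776, so error = 2Φ(−1.52) = 12.8%.

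**Full set, formula against simulation** (REML fit, null clinic-level predictor, 3,000 runs per cell):

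| Clinics | Method | c = 0 | 0.01 | 0.02 | 0.05 |
|---|---|---|---|---|---|
| 15 | formula | 5.0% | 8.2% | 11.2% | 18.7% |
| 15 | simulated | 5.2% | 8.0% | 12.0% | 18.4% |
| 25 | formula | 5.0% | 6.7% | 8.4% | 12.8% |
| 25 | simulated | 5.2% | 7.0% | 8.7% | 13.0% |
| 35 | formula | 5.0% | 6.1% | 7.2% | 10.0% |
| 35 | simulated | 5.8% | 6.4% | 7.5% | 10.0% |

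**Linked subset** (n = 221/50 = 4.42). For c from 0.01 to 0.05 the formula gives 6.0% to 9.6% with 15 clinics, 5.4% to 6.9% with 25 and 5.2% to 5.8% with 35. Simulation gave about 5-11%.

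**Subjective norms that leave out the clinician's own rate** are not exactly constant within a clinic. Simulated error in the full set with 25 clinics was still 9.3% at c = 0.02 and 13.3% at c = 0.05.

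**Is it only the 1.96 cutoff?** Using t with K − 2 degrees of freedom on the unchanged model at c = 0.05 gives 2Φ(−2.160 × 0.673) = 14.6% with 15 clinics and 2Φ(−2.069 × 0.776) = 10.8% with 25. In the linked subset with 15 clinics the same cutoff gives 2Φ(−2.160 × 0.850) = 6.6%. So the cutoff explains part of the excess, and most of it in the linked subset.

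**After the fix.** A clinic random intercept with small-sample degrees of freedom gave 5-6%. A simpler stand-in, regression on clinic means with K − 2 degrees of freedom, gave 4.2% to 6.0%.

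**The case against.** The strongest case against has five parts.

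- **The inflation is conditional.** With no residual variance between clinics the clinician-only model rejects at about 5-6%. The documents give neither the clinic ICC nor the number of clinics. A reader might infer that the standard errors are too small as a matter of fact; the documents do not support that. This stands. Equally, the plan gives no reason to assume zero clinic variance, and measuring norms by clinic supposes that clinics differ in practice.
- **Testing is inferred.** Table 2 has no column for aims, and the linked analysis speaks of physician-level and patient-level variables. That clinic size and subjective norms will be tested follows only from their place in the clinician-level block and the wording of Aim 1. A reader might infer that Hypothesis 1 is undermined; neither measure is in it. This stands. Hypothesis 1 factors are touched only through their own clustering: with an assumed within-clinic correlation of 0.3, a clinician-level predictor had 7-8% error.
- **The full-set layout is not documented.** The plan does not say that the 125 enrolled clinicians cared for all 553 patients, and it expects about 40% linkage. Models using surveyed clinician factors are confined to linked patients, where the effect is smaller. This stands, so both ranges are given.
- **Binary outcomes and model selection are less well covered.** A rough check with clinician-clustered GEE in place of the logistic mixed model (400 runs per cell) gave 5% at clinic ICC 0. At 0.05 it gave about 20% with 15 clinics and 11% with 25. AIC selection and the overall-model test were not part of the error rates above.
- **A clinic code may not be to hand.** The analysts hold de-identified data or a limited data set. This stands and belongs in the cost.

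**Conclusion.** The point holds in conditional form. Two measures listed as clinician factors sit at clinic level, and no model allows for clinics. If they are tested and outcomes vary between clinics, their standard errors will be too small.

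The size depends on quantities the plan omits. On the assumptions above, error ranges from nominal at clinic ICC 0 to about 19% in the full set (15 clinics, clinic ICC 0.05), and reaches about 11% in the linked subset. The documents do not establish that error does exceed 5%, nor that any named hypothesis is invalid. The change should be made before results for clinic-level factors are reported.

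**What to change.** In any linear or logistic model that includes a clinic-level predictor, add a clinic random intercept, so that patients are nested in clinicians and clinicians in clinics. Use Satterthwaite or Kenward-Roger degrees of freedom in the linear models. Report the number of clinics and the clinic ICC. Plain clinic-clustered sandwich errors are not a good substitute: with 15-25 clinics they gave about 10-12% error.

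The cost is a short addition to the analysis text, wider intervals for clinic-level factors, and a clinic variance that may estimate as zero. The analysis file must carry a coded clinic identifier. Clinic membership was needed to build subjective norms, but the documents do not show that a code reached the de-identified file, so a further data transfer may be required.

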3.3. Primary Objective

Aim 1. Use survey and EHR data to identify clinician factors that predict: a) patient-perceived lung cancer screening decision quality; b) screening completion among patients deciding to screen; and c) stage of readiness for smoking cessation among current smokers. *Hypothesis 1: Increased clinician knowledge, positive attitude toward lung cancer screening, positive attitude toward shared decision making (SDM), decreased clinician perceived barriers, and high lung cancer screening referral propensity predict higher decision quality, screening completion, and advances in stage of readiness for cessation.*

Aim 2. Use survey and EHR data to identify patient factors that predict: a) patient-perceived lung cancer screening decision quality; b) screening completion among patients deciding to screen; and c) stage of readiness for smoking cessation among current smokers. *Hypothesis 2: Patient-perceived stigma and medical mistrust predict decreased decision quality, screening completion, and advances in stage of readiness for cessation.*

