3.4. Primary Outcome Variable(s)

a) patient-perceived lung cancer screening decision quality; b) screening completion among patients deciding to screen; and c) stage of readiness for smoking cessation among current smokers

4 - Study Design

Please note the data for this study has already been collected at my prior institution and the only activity occurring at present is data analysis. The following is offered for context:

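### AIC selection is said to avoid type I error inflation, but neither AIC nor the overall test on the selected model provides that protection

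*Combined protocol and SAP*

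**What the plan says.** Section 5 (Methods, Quantitative Data Analysis and Interpretation) chooses the models for two of the three primary outcomes, decision quality and screening completion, by Akaike's "Information Criterion (AIC), instead of the usual statistical significance level (to avoid type I error inflation". It continues: "We will only consider the statistical significance of each independent variable in the final models if the corresponding overall model test is significant", with alpha 0.05 for that overall test.

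Section 3.3 names the factors of interest. Hypothesis 1 lists five clinician factors: "Increased clinician knowledge, positive attitude toward lung cancer screening, positive attitude toward shared decision making (SDM), decreased clinician perceived barriers", and referral propensity. Hypothesis 2 lists two patient factors: "Patient-perceived stigma and medical mistrust predict decreased decision quality, screening completion, and advances in stage of readiness for cessation". Sections 1 and 3.2 add a central hypothesis about discussions perceived as shared, which Table 2 (Section 5.5) measures with the SDM-Q-9.

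The plan does not list the candidates for selection, say whether the hypothesised factors are kept regardless of AIC, or mention any multiplicity adjustment.

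**The concern.** The plan gives error control as its reason for using AIC, and the 0.05 overall test looks like a second safeguard. A reader would take a factor reported as significant in a final model to have passed two protective steps. AIC is a criterion for predictive fit and has no type I error target, and an overall test on a selected model does not keep its nominal level. If neither protects, p-values for the main hypotheses on two primary outcomes would be given more weight than they can bear. There is a second risk: if the hypothesised factors compete for inclusion, a factor that is dropped has no estimate or interval.

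**Working it through.** The documents give no error rate for this procedure, so there is no figure of the plan's own to reproduce. Inputs from the documents: AIC selection, overall test at 0.05 on the final model, two-sided 0.05 per factor, five and two named factors (Section 3.3), 553 patients and 125 clinicians (Section 5). Candidate lists, correlations, ICC, and the size and event rate of the screening-completion subset are assumptions. Rates are per outcome and aim.

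**1. What AIC lets through.** AIC charges 2 per parameter, so a one-parameter term stays when its likelihood-ratio chi-square exceeds 2. P(chi-square with 1 df > 2) = 0.157. With independent candidates, any null factor at p<0.05 (chi-square > 3.84) has already passed AIC, so AIC removes no false positive. A null factor is dropped 1 - 0.157 = 84% of the time.

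**2. What the overall test stops.** Suppose the selected model has m terms, one of them at p<0.05. Its chi-square is at least 3.84 + 2(m - 1). For m = 1 to 5:
- minimum: 3.84, 5.84, 7.84, 9.84, 11.84
- 5% critical value: 3.84, 5.99, 7.81, 9.49, 11.07

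Only a two-term model can fail, and only narrowly.

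**3. Rates when nothing is associated.** Candidates are the named factors only, independent, none forced in; large-sample simulation, 1,000,000 draws.

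| | Two factors | Five factors |
|---|---|---|
| Overall test on AIC-selected model passes | 10.0% | 24.9% |
| At least one false correlate, plan's rule | 9.7% | 22.6% |
| At least one false correlate, unadjusted tests | 9.7% | 22.7% |
| Overall test on fixed full model passes | 5.0% | 5.0% |

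The formula agrees with the unadjusted row: 1 - 0.95^2 = 9.75% and 1 - 0.95^5 = 22.6%.

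**4. Robustness.**
- Correlation 0.3 to 0.7 among factors, plan's rule against unadjusted full-model tests: 9.4-9.9% against 8.4-9.8% (two); 23.3-23.9% against 21.4-21.9% (five).
- Random-intercept linear model, 553 patients in 125 clinicians, ICC 0.05: overall test passes 9.6% / 25.5%, any false correlate 9.3% / 23.8%.
- Random-intercept logistic model with an assumed 450 patients, 120 clinicians, latent ICC 0.05 and 75% completion: 10.8% / 26.5% and 10.4% / 23.1%.

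**5. Stigma and mistrust forced in, AIC choosing among other covariates.** With 5 others, or with the 15 other patient-level survey variables in Table 2 taken as candidates, the overall test passes 17% or 48% of the time. A false stigma or mistrust claim occurs 6.8% or 8.9% of the time. It is about 5% with no other candidates, or if the pair is tested jointly first.

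**6. What moving the overall test would do.** Take one truly associated factor with 80% individual power (expected z = 1.96 + 0.84 = 2.80) and the rest null. Chance of declaring it, two / five factors:
- plan's rule: 80% / 80%
- overall test on the full model or jointly on the factors: 70% / 54%
- Holm: about 71% / 59%. For two factors, P(z > 2.24) = 0.712, plus (0.800 - 0.712) x 0.025 = 0.002, gives 0.714.

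False correlates among the other four of five are about 19% under the plan (1 - 0.95^4 = 18.5%) and 15% with the full-model test. With two factors they are 5.0% and 4.8%.

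**The case against.** The strongest reply is that AIC is no worse than ordinary testing, that the study is descriptive, and that the headline rates need a reading the plan never states. Much of this stands. The excess is ordinary multiplicity that AIC fails to remove; a reader might infer that AIC creates it, and step 3 shows otherwise. A reader might also take 10% and 23% as the plan's actual error rates. They are not: Section 5 never says that the hypothesised factors compete for inclusion, and its power statement about adjusted effects fits keeping them in, which gives the smaller figures of step 5. Five is a count of named factors, not of variables; Table 2 splits barriers in two, for example.

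A second objection is that the obvious remedy, moving the overall test to a full model, costs power and helps little once any factor is real. Step 6 bears this out, so that move should not be presented as a cheap repair.

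A third possible inference is that the same problem affects the linked patient-provider analysis ("an estimated 40% of the total number of patients"). The plan does not state AIC for that secondary analysis, so the point is not extended to it.

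What does not stand is that the overall test rescues the rationale. The text ties it to the final models, which on the natural reading are those AIC selected; there it does not hold 5%.

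**Conclusion.** The stated reason for using AIC is wrong as written. On the competing-candidates reading, under the global null, the nominal 5% overall test passes about 10% (two factors) or 25% (five), and at least one false correlate appears about 10% or 23% of the time, matching unadjusted testing. On the forced-in reading for Hypothesis 2, the false-claim rate is about 7-9% with 5 to 15 assumed covariates. Both readings assume independent factors and that the overall test is run on the selected model; run on a prespecified full model it would hold 5%, but only when nothing is associated. The mechanism in steps 1 and 2 does not depend on sample size. The documents do not support a claim that AIC makes matters materially worse than unadjusted testing, or that any particular result is false. The results remain usable once the claimed protection is withdrawn.

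**What to change.** - Delete the statement that AIC avoids type I error inflation.
- For each of the two outcomes, make one prespecified model the main result, with a listed covariate set and the hypothesised factors forced in: the five clinician factors for Aim 1, stigma and mistrust for Aim 2, and SDM-Q-9 for the central hypothesis, so that it is not left as an optional covariate. Report every estimate with its interval.
- State that individual p-values are unadjusted for multiplicity and that the overall test on an AIC-selected model does not hold 5%.
- Label AIC-selected models exploratory.
- Data collection is complete and analysis is under way, so if outcome results have already been examined, say so and date the list.

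This does not lower the familywise rate. It removes a false assurance and guarantees an estimate for every hypothesised factor.

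**Cost.** Wording and one model per outcome and aim; no new data. Keeping all factors widens intervals somewhat. At an assumed common correlation of 0.3, R-squared is 0.09 for two factors and 4 x 0.09 / (1 + 3 x 0.3) = 0.19 for five, so standard errors grow by 1/sqrt(1 - R-squared) = 1.05 and 1.11. SDM-Q-9 and further covariates would add to this.

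**Optional.** The overall test on the full model, a joint test of the hypothesised factors, or Holm may be added if the team wants formal control and accepts the power loss in step 6. Of these, only Holm protects once some factor is truly associated.
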